9.3.5. Secondary Endpoint(s)/Estimand(s) Analysis

Objective	Estimands	Statistical Analysis Methods
Immunogenicity	
 GMC of IgG concentrations to each of the 20 vaccine serotypes 1 month after the last assigned vaccination in each group 	
 GMC and 2-sided 95% CI
	
 Percentage of participants with IgG concentrations to the 13vPnC serotypes with a predefined level^a 1 month after the last assigned vaccination in each group. 	
 Descriptive summary statistics •
	
 GMT of OPA titers to each of the 20 vaccine serotypes 1 month after the last assigned vaccination in each group 	
 GMT and 2-sided 95% CI

a. The predefined level is 0.35 µg/mL for all 13vPnC serotypes except serotypes 5, 6B, and 19A, which have predefined levels of 0.23, 0.10, and 0.12, respectively.

CCI

CCI		

9.4. Interim Analyses

No formal interim analysis will be conducted for this study.

9.5. Sample Size Determination

A total of approximately 360 participants will be randomized for approximately 315 evaluable participants, with an estimate of 105 evaluable participants per vaccine group.

The sample size of the study is determined primarily based on considerations of accumulating adequate data to evaluate the safety and immunogenicity of 1 or 2 doses of 20vPnC in healthy toddlers with 2 prior infant doses of 13vPnC.

Table 4 displays the lower 2-sided 95% confidence limit of the percentage of participants with predefined IgG concentrations for the primary immunogenicity endpoint. Assumed true proportions ranging from 80% to 100% are displayed in order to help quantify the expected precision assuming 105 evaluable participants in each vaccine group.

Table 4. Precision of Percentage of Participants With Predefined IgG Concentrations

Assumed True Proportion (%)	Lower 95% Confidence Limit of Proportion (%), 105 Evaluable Participants per Group
80	71
85	78
90	83
95	89
100	97

Abbreviation: IgG = immunoglobulin G.

[figure not shown]
Note: Lower confidence limits of 2-sided 95% CI are calculated using the Clopper and Pearson method, assuming the observed number of participants with predefined IgG concentrations is $105 \times$ true proportion.

The primary safety objective includes the endpoints for AEs reported within 1 month after the last assigned vaccination in each group. With 120 participants in each vaccine group, the probability of observing at least 1 AE in each is greater than 90%, assuming a true rate of at least 2% (Table 5).

Table 5. Probability of Observing an Event Given a Specified Incidence Rate and Assuming 120 Participants per Group

Sample Size	True Rate of AEs	Probability of Observing at Least 1 AE
120	1.0%	70.1%
120	2.0%	91.1%
120	5.0%	99.8%

PFIZER CONFIDENTIAL

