9.3.2. Analysis for Binary Data

Descriptive statistics for categorical variables (eg, proportions) are the percentage (%), the numerator (n) and the denominator (N) used in the percentage calculation, and the 2-sided 95% CIs where applicable.

The exact 95% CI for binary endpoints for each group will be computed using the F distribution (Clopper-Pearson).

Three-Tier Approach for AE Summary

A 3-tier approach will be used to summarize AEs. Under this approach, AEs are classified into 1 of 3 tiers:

1. Tier 1 events are prespecified events of clinical importance and are identified in a list in the product's safety review plan. There is no Tier 1 event identified for 20vPnC at this stage.
2. Tier 2 events are those that are not Tier 1 but are considered "relatively common"; a MedDRA preferred term is defined as a Tier 2 event if there are at least 4 participants in at least 1 vaccine group reporting the event.
3. Tier 3 events are those that are neither Tier 1 nor Tier 2 events.

For both Tier 1 (if any identified later) and Tier 2 events, the 95% CIs for the difference in percentage of participants reporting the events between each of the 20vPnC groups and the 13vPnC group will be calculated using the Miettinen and Nurminen method.

In addition, for Tier 1 events (if any identified later), the asymptotic p-values will also be presented for the difference in percentage of participants reporting the events between each of the 20vPnC groups and the 13vPnC group, based on the same test statistic and under the assumption that the test statistic is asymptotically normally distributed.

Descriptive summary statistics will be provided for Tier 3 events for each vaccine group.

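### Does the lower limit of 78 in the 85% row of Protocol Table 4 contradict the table's own note?

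*Protocol*

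**What the plan says.** Protocol section 9.5 plans about 360 randomized participants, "with an estimate of 105 evaluable participants per vaccine group". Table 4 translates that number into precision for the primary immunogenicity endpoint, the percentage of participants reaching the predefined IgG concentration. The assumed proportions "are displayed in order to help quantify the expected precision assuming 105 evaluable participants in each vaccine group".

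The table's note fixes the method and the count in one sentence: the lower limits of the 2-sided 95% interval are "calculated using the Clopper and Pearson method, assuming the observed number of participants with predefined IgG concentrations is" 105 × the true proportion. It does not say what happens when that product is not a whole number.

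The printed limits are 71, 78, 83, 89 and 97. The same exact method is planned for the analysis (Protocol section 9.3.2, SAP section 5.2.1). Protocol section 9.1.1 and SAP section 5.1 state that no hypothesis is tested.

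**The concern.** A reader who follows the note literally multiplies 105 by 0.85, enters 89.25 in the Clopper-Pearson formula and gets 76.7, which prints as 77. With the nearest whole count, 89, the result is 76.4, which prints as 76. Neither is the printed 78. The other four rows agree with the literal calculation, so the 85% row stands out as a single wrong cell. The printed distances from assumed proportion to lower limit (9, 7, 7, 6, 3) also look uneven.

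With no hypothesis test, this table is the plan's stated basis for precision on the primary immunogenicity endpoint. A wrong cell would make that precision look slightly better than the plan's own assumptions support.

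**Working it through.** **Inputs.** From Protocol section 9.5: n = 105 per group; 2-sided 95% Clopper-Pearson, so 0.025 in the lower tail; assumed proportions 80, 85, 90, 95 and 100%; printed limits 71, 78, 83, 89 and 97.

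**Formula.** For x responders out of n, the lower limit is the 0.025 quantile of a Beta(x, n − x + 1) distribution. For x = n it reduces to 0.025^(1/n). With n = 105 this is 0.025^(1/105) = 0.9655, which reproduces the printed 97 in the last row.

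**Counts.** The products 105 × p are 84, 89.25, 94.5, 99.75 and 105. Three of the five are not whole, so some rule is needed to turn them into participants. The results under each rule, in percent, are:

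| True proportion | Printed | Fractional x | Rounded down | Nearest whole (halves up) | Rounded up |
|---|---|---|---|---|---|
| 80 | 71 | 71.07 (x = 84) | 71.07 (84) | 71.07 (84) | 71.07 (84) |
| 85 | 78 | 76.71 (89.25) | 76.44 (89) | 76.44 (89) | 77.53 (90) |
| 90 | 83 | 82.60 (94.5) | 82.03 (94) | 83.18 (95) | 83.18 (95) |
| 95 | 89 | 88.92 (99.75) | 87.98 (99) | 89.24 (100) | 89.24 (100) |
| 100 | 97 | 96.55 (105) | 96.55 (105) | 96.55 (105) | 96.55 (105) |
| Rows matched | | 4 of 5 | 2 of 5 | 4 of 5 | 5 of 5 |

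Rounding up is the only one of these rules that returns the whole printed table.

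**Do the other four rows favour the fractional reading?** No. At 80% and 100% the product is already whole. At 90% the fractional and rounded-up limits (82.60 and 83.18) both print as 83. At 95% (88.92 and 89.24) both print as 89. These four rows fit both readings equally well.

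**Is 77 attainable?** Not with whole participants: 89/105 gives 76.44 and 90/105 gives 77.53. Replacing 78 by 77 would put in a value that no observed result at n = 105 can produce.

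**Are the uneven distances a sign of error?** No. Measured from the labelled proportion, the rounded-up limits lie 8.93, 7.47, 6.82, 5.76 and 3.45 points below it. Measured from the proportion each count represents (84/105 = 80.00%, 90/105 = 85.71%, 95/105 = 90.48%, 100/105 = 95.24%, 105/105 = 100%), the distances are 8.93, 8.18, 7.29, 6.00 and 3.45, a smooth decline. The unevenness comes from labelling the rows with round proportions and printing whole percents.

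**Could another interval method explain the table instead?** At n = 105 with fractional counts, Wald gives 78.17 at 85% but 72.35 at 80%, where 71 is printed. One-sided 95% Clopper-Pearson gives 78.05 and 72.49, with the same misfit. Wilson gives 76.94 at 85%. None of them reproduces the table, whereas the stated method with rounded-up counts does.

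**The case for a change.** The strongest reply is that the five-of-five match proves less than it seems to. Only the 85% row separates rounding up from the fractional or nearest-whole count, so using that row to infer the rule that justifies it is circular. The note does not mention rounding up, and 89/105 = 84.8% is closer to 85% than 90/105 = 85.7%. The departure is also in the favourable direction.

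Part of this stands. The rounding rule cannot be proved from the documents. The note is silent on it, and the row labelled 85% in effect shows the limit for 85.7%.

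It does not establish an error, though. To call the cell wrong, one must show that the stated method cannot give 78. It can, with a whole number of participants and one rule applied to every row. The alternative needs a fractional participant in three rows and a separate slip in the fourth non-matching cell that happens to equal the 90/105 value. The 90% and 95% rows also rule out rounding down without any appeal to the 85% row, since they would then print 82 and 88.

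**Conclusion.** The concern does not hold. The printed 78 is the 2-sided 95% Clopper-Pearson lower limit for 90 of 105 participants, and rounding the product up to whole participants reproduces all five rows of Table 4. This rests on reading the note's observed number as a whole number of participants, and on rounding up as the rule, which the protocol does not state but which alone among the rules tried fits every row.

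The residue is a missing detail in a table note. The 85% row stands 0.8 points above the fractional-count limit (77.53 against 76.71) and 1.1 points above the nearest-whole-count limit (77.53 against 76.44), or 1 to 2 points as printed. Table 4 illustrates precision and drives no test or decision rule. Whichever convention is used, the target of 105 evaluable participants per group, the planned exact intervals and the interpretation of the trial stay the same.

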10. SUPPORTING DOCUMENTATION AND OPERATIONAL CONSIDERATIONS

10.1. Appendix 1: Regulatory, Ethical, and Study Oversight Considerations

10.1.1. Regulatory and Ethical Considerations

This study will be conducted in accordance with the protocol and with the following:

- Consensus ethical principles derived from international guidelines, including the Declaration of Helsinki and CIOMS International Ethical Guidelines;
- Applicable ICH GCP guidelines;
- Applicable laws and regulations, including applicable privacy laws.

The protocol, protocol amendments, ICD, SRSD(s), and other relevant documents (eg, advertisements) must be reviewed and approved by the sponsor, submitted to an IRB/EC by the investigator, and reviewed and approved by the IRB/EC before the study is initiated.

Any amendments to the protocol will require IRB/EC approval before implementation of changes made to the study design, except for changes necessary to eliminate an immediate hazard to study participants.

Protocols and any substantial amendments to the protocol will require health authority approval prior to initiation except for changes necessary to eliminate an immediate hazard to study participants.

The investigator will be responsible for the following:

- Providing written summaries of the status of the study to the IRB/EC annually or more frequently in accordance with the requirements, policies, and procedures established by the IRB/EC;
- Notifying the IRB/EC of SAEs or other significant safety findings as required by IRB/EC procedures;
- Providing oversight of the conduct of the study at the site and adherence to requirements of 21 CFR, ICH GCP guidelines, the IRB/EC, European regulation 536/2014 for clinical studies (if applicable), European Medical Device Regulation 2017/745 for clinical device research (if applicable), and all other applicable local regulations.

10.1.1.1. Reporting of Safety Issues and Serious Breaches of the Protocol or ICH GCP

In the event of any prohibition or restriction imposed (ie, clinical hold) by an applicable regulatory authority in any area of the world, or if the investigator is aware of any new information that might influence the evaluation of the benefits and risks of the study intervention, Pfizer should be informed immediately.

In addition, the investigator will inform Pfizer immediately of any urgent safety measures taken by the investigator to protect the study participants against any immediate hazard, and of any serious breaches of this protocol or of the ICH GCP guidelines that the investigator becomes aware of.

10.1.2. Financial Disclosure

Investigators and subinvestigators will provide the sponsor with sufficient, accurate financial information as requested to allow the sponsor to submit complete and accurate financial certification or disclosure statements to the appropriate regulatory authorities. Investigators are responsible for providing information on financial interests during the course of the study and for 1 year after completion of the study.

10.1.3. Informed Consent Process

The investigator or his/her representative will explain the nature of the study, including the risks and benefits, to the participant's parent(s)/legal guardian(s) and answer all questions regarding the study. The participant's legally authorized representative should be given sufficient time and opportunity to ask questions and to decide whether or not to participate in the trial.

[figure not shown]
[figure not shown]
Participants' parent(s)/legal guardian(s) must be informed that their participation is voluntary. Participants' parent(s)/legal guardian(s) will be required to sign a statement of informed consent that meets the requirements of 21 CFR 50, local regulations, ICH guidelines, privacy and data protection requirements, where applicable, and the IRB/EC or study center.

The investigator must ensure that each study participant's parent(s)/legal guardian(s) is fully informed about the nature and objectives of the study, the sharing of data related to the study, and possible risks associated with participation, including the risks associated with the processing of the participant's personal data.

The participant's parent(s)/legal guardian(s) must be informed that the participant's personal study-related data will be used by the sponsor in accordance with local data protection law. The level of disclosure must also be explained to the participant's parent(s)/legal guardian(s).

The participant's parent(s)/legal guardian(s) must be informed that the participant's medical records may be examined by Clinical Quality Assurance auditors or other authorized personnel appointed by the sponsor, by appropriate IRB/EC members, and by inspectors from regulatory authorities.

PFIZER CONFIDENTIAL

The investigator further must ensure that each study participant's parent(s)/legal guardian(s) is fully informed about his or her right to access and correct the participant's personal data and to withdraw consent for the processing of the participant's personal data.

The medical record must include a statement that written informed consent was obtained before the participant was enrolled in the study and the date on which the written consent was obtained. The authorized person obtaining the informed consent must also sign the ICD.

The participant's parent(s)/legal guardian(s) must be reconsented to the most current version of the ICD(s) during their participation in the study.

A copy of the ICD(s) must be provided to the participant's parent(s)/legal guardian(s).

10.1.4. Data Protection

All parties will comply with all applicable laws, including laws regarding the implementation of organizational and technical measures to ensure protection of participant data.

Participants' personal data will be stored at the study site in encrypted electronic and/or paper form and will be password protected or secured in a locked room to ensure that only authorized study staff have access. The study site will implement appropriate technical and organizational measures to ensure that the personal data can be recovered in the event of disaster. In the event of a potential personal data breach, the study site will be responsible for determining whether a personal data breach has in fact occurred and, if so, providing breach notifications as required by law.

To protect the rights and freedoms of participants with regard to the processing of personal data, participants will be assigned a single, participant-specific numerical code. Any participant records or data sets that are transferred to the sponsor will contain the numerical code; participant names will not be transferred. All other identifiable data transferred to the sponsor will be identified by this single, participant-specific code. The study site will maintain a confidential list of participants who participated in the study, linking each participant's numerical code to his or her actual identity and medical record ID. In case of data transfer, the sponsor will protect the confidentiality of participants' personal data consistent with the clinical study agreement and applicable privacy laws.

[figure not shown]
[figure not shown]
10.1.5. Committees Structure

10.1.5.1. Data Monitoring Committee

This study will use a DMC. The DMC is independent of the study team and includes only external members. The DMC charter describes the role of the DMC in more detail.

The DMC will be responsible for ongoing monitoring of the safety of participants in the study according to the charter. The recommendations made by the DMC will be forwarded to the appropriate authorized Pfizer personnel for review and final decision. Pfizer will

PFIZER CONFIDENTIAL

communicate such decisions, which may include summaries of aggregate analyses of safety data to regulatory authorities, investigators, as appropriate.

10.1.6. Dissemination of Clinical Study Data

Pfizer fulfills its commitment to publicly disclose clinical study results through posting the results of studies on www.clinicaltrials.gov (ClinicalTrials.gov), the EudraCT, and/or www.pfizer.com, and other public registries in accordance with applicable local laws/regulations. In addition, Pfizer reports study results outside of the requirements of local laws/regulations pursuant to its SOPs.

In all cases, study results are reported by Pfizer in an objective, accurate, balanced, and complete manner and are reported regardless of the outcome of the study or the country in which the study was conducted.

www.clinicaltrials.gov

Pfizer posts clinical trial results on www.clinicaltrials.gov for Pfizer-sponsored interventional studies (conducted in patients) that evaluate the safety and/or efficacy of a product, regardless of the geographical location in which the study is conducted. These results are submitted for posting in accordance with the format and timelines set forth by US law.

[EudraCT](http://www.eudra-ct.info)

Pfizer posts clinical trial results on EudraCT for Pfizer-sponsored interventional studies in accordance with the format and timelines set forth by EU requirements.

[figure not shown]
[figure not shown]
www.pfizer.com

Pfizer posts public disclosure synopses (CSR synopses in which any data that could be used to identify individual participants have been removed) on www.pfizer.com for Pfizer-sponsored interventional studies at the same time the corresponding study results are posted to www.clinicaltrials.gov.

Documents within marketing authorization packages/submissions

Pfizer complies with the European Union Policy 0070, the proactive publication of clinical data to the EMA website. Clinical data, under Phase 1 of this policy, includes clinical overviews, clinical summaries, CSRs, and appendices containing the protocol and protocol amendments, sample CRFs, and statistical methods. Clinical data, under Phase 2 of this policy, includes the publishing of individual participant data. Policy 0070 applies to new marketing authorization applications submitted via the centralized procedure since 01 January 2015 and applications for line extensions and for new indications submitted via the centralized procedure since 01 July 2015.

PFIZER CONFIDENTIAL

Data sharing

Pfizer provides researchers secure access to patient-level data or full CSRs for the purposes of “bona-fide scientific research” that contributes to the scientific understanding of the disease, target, or compound class. Pfizer will make data from these trials available 24 months after study completion. Patient-level data will be anonymized in accordance with applicable privacy laws and regulations. CSRs will have personally identifiable information redacted.

Data requests are considered from qualified researchers with the appropriate competencies to perform the proposed analyses. Research teams must include a biostatistician. Data will not be provided to applicants with significant conflicts of interest, including individuals requesting access for commercial/competitive or legal purposes.

10.1.7. Data Quality Assurance

All participant data relating to the study will be recorded on printed or electronic CRF unless transmitted to the sponsor or designee electronically (eg, laboratory data). The investigator is responsible for verifying that data entries are accurate and correct by physically or electronically signing the CRF.

Guidance on completion of CRFs will be provided in the CRF Completion Requirements document.

[figure not shown]
[figure not shown]
The investigator must ensure that the CRFs are securely stored at the study site in encrypted electronic and/or paper form and are password protected or secured in a locked room to prevent access by unauthorized third parties.

QTLs are predefined parameters that are monitored during the study. Important deviations from the QTLs and any remedial actions taken will be summarized in the clinical study report.

The investigator must permit study-related monitoring, audits, IRB/EC review, and regulatory agency inspections and provide direct access to source data documents. This verification may also occur after study completion. It is important that the investigator(s) and their relevant personnel are available during the monitoring visits and possible audits or inspections and that sufficient time is devoted to the process.

Monitoring details describing strategy, including definition of study critical data items and processes (eg, risk-based initiatives in operations and quality such as risk management and mitigation strategies and analytical risk-based monitoring), methods, responsibilities, and requirements, including handling of noncompliance issues and monitoring techniques (central, virtual, or on-site monitoring), are provided in the data management plan and monitoring plan maintained and utilized by the sponsor or designee.

PFIZER CONFIDENTIAL

The sponsor or designee is responsible for the data management of this study, including quality checking of the data.

Records and documents, including signed ICDs, pertaining to the conduct of this study must be retained by the investigator for 15 years after study completion unless local regulations or institutional policies require a longer retention period. No records may be destroyed during the retention period without the written approval of the sponsor. No records may be transferred to another location or party without written notification to the sponsor. The investigator must ensure that the records continue to be stored securely for as long as they are maintained.

When participant data are to be deleted, the investigator will ensure that all copies of such data are promptly and irrevocably deleted from all systems.

The investigator(s) will notify the sponsor or its agents immediately of any regulatory retain notification in relation to the study. Furthermore, the investigator will cooperate with the sponsor or its agents to prepare the investigator site for the inspection and will allow the sponsor or its agent, whenever feasible, to be present during the inspection. The investigator site and investigator will promptly resolve any discrepancies that are identified between the study data and the participant's medical records. The investigator will promptly provide copies of the inspection findings to the sponsor or its agent. Before response submission to the regulatory authorities, the investigator will provide the sponsor or its agents with an opportunity to review and comment on responses to any such findings.

